## PROTOCOL AMENDMENT SUMMARY

The following is a list of key changes of **no substantial** protocol clarifications to the APD334-006 Protocol Amendment 01 dated 11 April 2017.

[figure not shown]
Section(s) Amended	Description of Changes made
Synopsis	Deleted sentence “Diagnosis of active psoriasis, erythema nodosum or pyoderma gangrenosum by Investigator assessments. <del>After the enrollment of 10 patients with active EIM, patients with active psoriasis due to anti-TNF-alpha therapy can also be included.</del> ”
4.1 Study Population	Deleted sentence “Adult men and women, ages 18-80 years, who have mild, moderate or severe UC or CD with active skin extra-intestinal manifestations including pyoderma gangrenosum, erythema nodosum or psoriasis. <del>After the enrollment of 10 patients with active EIM, also patients with psoriasis due to anti-TNF-alpha treatment can be enrolled into the study.</del> ”
Synopsis Sample Size	Changed “10-20 patients” to: current: “Up to 20 patients (with up to 10 patients with anti TNF-alpha induced psoriasis)”
3.1 Overall Study Design and Plan	Study number corrected “APD334-003 is an open-label, ...” to: current “APD334-006 is an open label, ....”
3.1 Overall Study Design and Plan	Changed “Between 10 to 20 IBD patients with acute psoriasis, pyoderma gangrenosum or erythema nodosum will be included in the study. In these patients, psoriasis cannot be triggered by anti-TNF-alpha. However, after the enrollment of 10 patients, IBD patients with psoriasis due to anti-TNF-alpha treatment can be included to the study” to: current “Up to 20 IBD patients with acute psoriasis, pyoderma gangrenosum or erythema nodosum (with up to 10 patients with anti TNF-alpha induced psoriasis) will be included in the study”.

## SYNOPSIS

Name of Drug:	Etrasimod (APD334)
Indication	Inflammatory Bowel Disease (IBD) with active skin extra-intestinal manifestations (EIM) including Psoriasis, Erythema Nodosum (EN), and Pyoderma Gangrenosum (PG)
Sponsor:	Arena Pharmaceuticals, Inc. [name]
Name of Sponsor Contact	██████████ MD CMO Research and Development Arena Pharmaceuticals, Inc. [name] Phone: ██████████ email: ██████████
Name of Principal Investigator(s):	Multi-center
Medical Monitor:	██████████, MD Medical Monitor Arena Arena Pharmaceuticals, Inc. [name] Phone: ██████████ email: ██████████
Test Product, Dose and Mode of Administration:	
 
• ██████████ etrasimod once daily (q.d.) for 12 weeks
 
• Patients should be instructed to take their tablet on an empty stomach (after overnight fast) and to avoid eating for 1 hour after dosing. Patients should be advised not to crush, break, chew, or dissolve the tablet and to take study medication with an adequate amount of water.
 

Concurrent Control:	None. This is an open-label study.
Objectives:	The efficacy objective is to determine the treatment effect of etrasimod in Inflammatory Bowel Disease patients on the clinical improvement of active skin extra-intestinal manifestations. The safety objective is to determine the safety profile and tolerability of etrasimod.
Study Design	This is a phase 2a, proof-of-concept, multicenter, open-label, single-arm study in 10-20 IBD patients with active skin extra-intestinal manifestations. All visits in the study are ambulatory visits. The screening period

will last up to 4 weeks and is followed by a 12-week treatment period. During this treatment period patients will take one tablet of study medication once per day. The last dose is planned to be taken one day before the last treatment visit at week 12. A follow-up visit will take place 2 weeks after the end of treatment.

Study Site(s)	This study will be conducted in approximately 3 clinical centers.
Patient Population:	
Inclusion Criteria
 

1. Men or women of age 18 to 80 years, inclusive.

2. Able to give signed informed consent and willing and able to comply with the study requirements.

3. Considered to be in stable health in the opinion of the investigator as determined by:

a.) A pre-study physical examination with no clinically significant abnormalities unrelated to IBD.

b.) Vital signs (VS) at screening: pulse rate <math>\geq</math> 55 bpm, systolic blood pressure (SBP) <math>\geq</math> 90, and diastolic blood pressure (DBP) <math>\geq</math> 55 mmHg.

c.) Liver function tests (ALT/AST, bilirubin and alkaline phosphatase) <math><</math> 2x the upper limit of normal [ULN].

d.) All other pre-study clinical laboratory findings within normal range, or if outside of the normal range are not deemed clinically significant in the opinion of the investigator.

e.) 12-lead electrocardiogram (ECG) showing no clinically significant abnormalities in the opinion of the investigator (for confirmation please refer to exclusion criteria # 22).

f.) A chest x- ray showing no evidence of active pulmonary disease (a chest x-ray taken within the previous 12 months from the screening visit may also be used).

g.) Ophthalmology evaluation (by an ophthalmologist) without evidence of macular edema, supported with OCT where available (dependent on site capability) no later than 3 months prior to screening.

4. Patients receiving stable treatment for IBD and EIM as defined in section 6.12.

5. Diagnosis of active psoriasis, erythema nodosum or pyoderma gangrenosum by Investigator assessments.

6. Diagnosis of ulcerative colitis (UC) or Crohn's disease (CD) established prior to screening by clinical and endoscopic evidence.

7. Eligible female patients must be:

a.) non-pregnant, evidenced by a negative serum human chorionic gonadotropin (hCG) pregnancy test at screening and a urine dipstick pregnancy test at Day 1.

	
b.) non-lactating.
 
c.) sexually abstinent (if this is the preferred and usual lifestyle of the individual). Periodic abstinence (calendar, symptothermal, post-ovulation methods), withdrawal (coitus interruptus), and lactational amenorrhoea method are not acceptable methods of contraception.
 
d.) surgically sterile or postmenopausal or agree to continue to use an accepted method of birth control during and for at least 30 days after last study medication administration. Acceptable methods of birth control are:
 

- combined (estrogen and progestogen containing) hormonal contraception associated with inhibition of ovulation

o oral

o intravaginal

o transdermal

- progestogen-only hormonal contraception associated with inhibition of ovulation

o oral

o injectable

o implantable

- intrauterine device (IUD)

- intrauterine hormone-releasing system (IUS)

 
patients should be consistently taking the hormonal contraceptive for at least 3 months [90 days] prior to screening);
 

- surgical sterility for at least 6 months prior to screening for tubal ligation performed laparoscopically, hysterectomy and/or bilateral oophorectomy; and/or postmenopausal (defined as at least 2 years without menses).

 
Contraceptive measures, such as Plan B (used after unprotected sex), are not acceptable methods of contraception for this study.
 
8. Eligible male patients will either be:
 

- surgically sterile (i.e., vasectomy), for at least 3 months (90 days) prior to screening

 
or
 

- when sexually active with a female partner, the partner must be either surgically sterile, postmenopausal, or agree to continue to use an accepted method of birth control during and for at

--	---

	
least 30 days after last study medication administration as defined in 7 above. Please note that the use of condoms is an acceptable method of contraception for this study.
 
9. Eligible male and female patients must agree not to participate in a conception process (i.e. active attempt to become pregnant or to impregnate, sperm donation, in vitro fertilization) for 30 days after the last dose of study drug.
 
Exclusion Criteria:
 

1. Evidence of abdominal abscess or toxic megacolon at the screening visit.

2. Patients with history of extensive colitis or pancolitis of > 8 years duration or left-sided colitis of > 12 years duration must have documented evidence that a surveillance colonoscopy was performed within 12 months of the initial screening visit (if not, the patient should undergo a colonoscopy in lieu of a flexible proctosigmoidoscopy during screening).

3. Previous extensive colonic resection (subtotal or total colectomy).

4. Current evidence of adenomatous colonic polyps that have not been removed.

5. Current evidence of colonic mucosal dysplasia.

6. Ileostomy, colostomy, or known fixed symptomatic stenosis of the intestine or stoma.

7. Clinical significant infection as judged by the investigator in the previous 6 weeks before enrollment.

8. Evidence of or treatment for C. difficile infection within 60 days or other intestinal pathogen within 30 days prior to randomization.

9. Within 5 half-lives prior to randomization exposure to natalizumab or rituximab.

10. Within 30 days prior to randomization, treatment of underlying disease other than those specifically listed in Section 6.12.

11. Within 30 days or 5 half-lives (whichever is longer) prior to randomization receipt of any investigational agent.

12. Currently require or are anticipated to require surgical intervention for IBD during the study.

13. FEV1 or FVC < 80% of predicted values (i.e., abnormal).

14. Infection with the Hepatitis B or C virus.

15. Active or latent tuberculosis, regardless of treatment history, as evidenced by any of the following:

--	--

	

a. History of tuberculosis (that has not been successfully treated)

b. A positive diagnostic tuberculosis (TB) test within one month of randomization defined as a positive QuantiFERON® test or 2 successive indeterminate QuantiFERON tests

c. Chest X-ray within 12 months of randomization in which active or latent pulmonary tuberculosis cannot be excluded.

 

16. Any known history of congenital or acquired immunodeficiency (e.g., common variable immunodeficiency, human immunodeficiency virus [HIV] infection [ELISA and Western blot] test result, organ transplantation).

17. Clinically significant extra-intestinal infection (e.g., pneumonia, pyelonephritis) within 30 days prior to randomization.

18. Recent history (within 6 months of screening visit) of cardio or cerebrovascular disease, ACS, MI, unstable angina, CVA, TIA at screening.

19. Any surgical procedure requiring general anesthesia within 30 days prior to randomization or plans to undergo major surgery during the study period.

20. History of retinal macular edema.

21. History of or signs and symptoms of progressive multifocal leukoencephalopathy (PML) as assessed by the PML checklist.

22. History of cardiac arrhythmia, conduction system disease (including AV node dysfunction, 2nd or 3rd degree heart block, and sick sinus syndrome), or use of Class Ia and Class III anti-arrhythmic agents, or baseline QTc <math>\geq</math> 500 msec.

23. Infection requiring hospitalization or intravenous antimicrobial therapy, or opportunistic infection within 4 weeks of screening.

24. History of more than one episode of herpes zoster or any episode of disseminated zoster.

25. Without documented positive varicella zoster virus (VZV) IgG antibody status or who have completed VZV vaccination within 30 days prior to randomization.

26. Receipt of live vaccine within 4 weeks prior to screening.

27. History of lymphoproliferative disorder, lymphoma, leukemia, myeloproliferative disorder, or multiple myeloma.

28. History of malignancy except for adequately treated basal cell skin cancer.

29. History of severe allergic or anaphylactic reactions requiring medical attention.

30. Current or recent history (within one year prior to randomization) of alcohol dependence or illicit drug use.

31. History of clinically significant leukopenia or lymphopenia at screening.

32. Active psychiatric problems that, in the investigator's opinion,

--	---

	
may interfere with compliance with the study procedures.
 
33. History of any clinically significant medical condition that, in the investigator's opinion, would preclude participation in the study.
 
34. Use of moderate to strong inhibitors of CYP2C9.
 
35. History of severe renal or hepatic impairment.
 
36. Inability to attend all the study visits or comply with study procedures.
 
37. Prior exposure of etrasimod.

Duration per Patient:	Up to 18 weeks total: up to 4 weeks for screening, followed by a 12-week treatment period and a follow-up visit 2 weeks after the end of treatment.
Sample Size:	Up to 20 patients (with up to 10 patients with anti TNF-alpha induced psoriasis).
Efficacy Endpoints:	
As this is a proof-of-concept study, all endpoints are exploratory.
 
 
- UC endpoint: Change from baseline in stool frequency, rectal bleeding, PGA (Physicians Global Assessments) at weeks 1, 2, 4, 8 and 12.
 
- CD endpoint: Change from baseline in disease activity score at week 1, 2, 4, 8 and 12.
 
- Change from baseline in endoscopic improvement/histologic healing using endoscopy or flexible proctosigmoidoscopy. (Only if there are signs of inflammation at screening another evaluation will be performed at week 12).
 
- Change from baseline in level of fecal calprotectin at week 4, 8 and 12.
 
- Change from baseline in Physician Global Assessments for active skin extra-intestinal manifestations (PG, EN and psoriasis) at week 1, 2, 4, 8 and 12.
 
- Change from baseline in Patients Global Assessments for active skin extra-intestinal manifestations (PG, EN and psoriasis) at week 1, 2, 4, 8 and 12.
 
- Change from baseline in the Dermatology Life Quality Index (DLQI) score at week 1, 2, 4, 8 and 12.
 
- Psoriasis endpoint only (all other endpoints are for all skin manifestations): Change from baseline in Psoriasis
 

	
Area and Severity Index (PASI) score at week 1, 2, 4, 8 and 12.
 
 
- Change from baseline in Inflammatory Bowel Disease Questionnaire (IBDQ) score at week 2, 4, 8 and 12.
 
- Skin punch biopsies (from healthy skin and from target lesion) will be collected before treatment and at week 8 or 12. Immunohistochemistry and other analyzing methods such as RT-PCR will be performed to evaluate immune cell infiltration, cytokine expression in the skin and other inflammatory parameters.
 
- Change from baseline in C - reactive protein (CRP) at Weeks 1, 2, 4, 8 and 12.
 
- Chang from baseline in leucocyte characterization.
 
- Change from baseline in lymphocyte counts at Weeks 1, 2, 4, 8 and 12.
 

Safety Assessments:
	
 
- Clinical laboratory tests (chemistry, hematology and urinalysis)
 
- Vital sign measurements
 
- Physical examination
 
- 12-lead electrocardiograms (ECGs)
 
- Adverse event reporting
 
- Concomitant medication
 
- Lymphocyte counts
 

Statistical Analyses:
	
There is no formal sample size estimation for this proof-of-concept open label study. Sample size of 10 - 20 subjects is reasonable to assess proof-of-concept of the efficacy of etrasimod in the target population. Summary statistics will be provided to describe efficacy and safety measures. Confidence interval of key efficacy measures will be also produced for non-inferential comparisons with historical data.

Date
	
11 April 2017

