### **4.2 Inclusion and Exclusion Criteria**

Each patient must meet the inclusion and exclusion criteria described in the synopsis to be enrolled in the study.

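### Inclusion criterion 9 bars conception attempts, sperm donation and IVF only after the last dose and omits the 12 weeks of dosing; criteria 7d and 8 leave only a narrow gap

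*Combined protocol and SAP*

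**What the plan says.** All of the eligibility text is in the protocol Synopsis, and section 4.2 makes it binding: "Each patient must meet the inclusion and exclusion criteria described in the synopsis to be enrolled in the study".

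- **Criterion 9** (men and women): patients "must agree not to participate in a conception process (i.e. active attempt to become pregnant or to impregnate, sperm donation, in vitro fertilization"). The stated period is 30 days after the last dose. The sentence is complete and nothing in it is blacked out.
- **Criterion 7d** (women): those who are neither sterile by surgery nor past menopause must "agree to continue to use an accepted method of birth control during and for at least 30 days after last study medication administration". Surgical sterility must have been in place "for at least 6 months prior to screening for tubal ligation performed laparoscopically, hysterectomy and/or bilateral oophorectomy".
- **Criterion 8** (men): vasectomy at least 3 months before screening. Failing that, the rule is "when sexually active with a female partner, the partner must be either surgically sterile, postmenopausal, or agree to continue to use an accepted method", and the method must be used over the same period as in 7d. Condoms are accepted.
- **Criterion 7a** (women): "non-pregnant, evidenced by a negative serum human chorionic gonadotropin (hCG) pregnancy test at screening and a urine dipstick pregnancy test at Day 1".
- **Section 6.11.2.1**: a patient who becomes pregnant is discontinued at once, and pregnancies are reportable from Day 1 through Week 12 and up to 30 days after the last dose.

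**The concern.** Read literally, the agreement in criterion 9 starts only when dosing stops. A reproductive safeguard that applies after exposure but not during it has no evident rationale, and the protocol offers none. Criterion 9 is also the only readable provision that names sperm donation and IVF. If it does not cover dosing, no other readable text expressly bars those two activities while the patient is on the investigational drug. A site that takes the patient's agreement from the criterion as printed would obtain a commitment for the month after treatment only. What is at stake is patient and fetal safety and the accuracy of what patients agree to, not any estimate or test.

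**Working it through.** The plan gives no figure to reproduce. The check compares time periods and then asks who falls between the criteria.

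**Step 1: the periods side by side.**

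| Provision | What it governs | Dosing covered? | 30 days after covered? |
|---|---|---|---|
| Criterion 7d | Birth control, female patients | Yes | Yes |
| Criterion 8 | Birth control, partners of male patients | Yes | Yes |
| Section 6.11.2.1 | Reporting of pregnancies | Yes, from Day 1 | Yes |
| Criterion 9 | Conception attempts, sperm donation, IVF | No | Yes |

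Criterion 9 is the only one of the four without the treatment period.

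**Step 2: the length of the omitted period.** The Synopsis says: "The last dose is planned to be taken one day before the last treatment visit at week 12". The day number of that visit is an assumption here. If it is Day 85 (12 × 7 + 1), the last dose is on Day 84 and there are 84 dosing days; if it is Day 84, there are 83. The period in 7d and 8 is then 84 + 30 = 114 days, or 83 + 30 = 113 days. Criterion 9 covers the final 30 of these and none of the 83 to 84 dosing days.

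**Step 3: what 7d and 8 already prevent.** A fertile woman must use accepted birth control throughout dosing. A sexually active man without a vasectomy must have a female partner who is sterile, postmenopausal or covered by birth control throughout dosing. An active attempt to conceive by intercourse is therefore incompatible with 7d or 8 for most patients.

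**Step 4: what they do not reach.** Both criteria regulate contraception. Neither mentions donation or assisted reproduction.

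- *Men without a vasectomy.* Criterion 8 places a condition on a female partner, and only when the man is sexually active with one. A man with no female partner, or with a partner who meets the condition, can satisfy criterion 8 and still donate sperm during dosing. A man whose partner is surgically sterile by tubal ligation can satisfy it and still take part in IVF.
- *Women exempt from birth control.* A woman with a tubal ligation, or a postmenopausal woman, satisfies 7d with no birth-control duty. Neither status in itself excludes IVF.

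**Step 5: other readable safeguards.** The pregnancy tests in 7a are done at screening and Day 1, so they establish status at entry but say nothing about later weeks. Discontinuation under section 6.11.2.1 takes effect once a pregnancy exists. Neither provision prohibits donation or IVF during dosing.

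**The case against.** The strongest reply is that the intent is plain. Three neighbouring provisions cover treatment plus 30 days, and an investigator reading criteria 7 to 9 together is unlikely to conclude that IVF or sperm donation is permitted on drug and forbidden afterwards. This stands as an argument about weight. It does not correct the stated period, and it also shows that the authors wrote out the treatment period elsewhere when they meant it to apply.

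A second reply is that sections 5.1 to 5.3, 6.5, 6.8 to 6.10, 6.12 and 7, the schedule of procedures and the consent form cannot be read in the public copy and may contain an on-treatment restriction. That is possible, and it limits any claim about actual protection. It would not change criterion 9, which would then disagree with that text.

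Three stronger readings are tempting and are not supported:

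- A reader might infer that patients are free to try to conceive while on the drug. For most patients 7d and 8 prevent this.
- A reader might set the 30 days of criterion 9 against the 113 to 114 days of 7d and 8 and treat the difference as unprotected time. The difference describes the wording of one sentence; the contraception duty runs through the whole period.
- A reader might add women who qualify as "sexually abstinent (if this is the preferred and usual lifestyle of the individual") to the group left uncovered. That requires 7c to be an alternative to 7d. As printed, items a to d follow one another with no *or* between c and d, so 7d still applies to an abstinent woman on a literal reading.

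**Conclusion.** The point holds as a minor patient-safety correction. The period in criterion 9 is wrong as written: it leaves out all of the dosing period, and the criterion is operative. The gap that remains after 7d and 8 is narrow. It is mainly sperm donation or IVF participation by men without a vasectomy, and IVF in women exempt from birth control under 7d. These are the main routes rather than a complete list.

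The documents do not say how many patients could be affected. With at most 20 enrolled, the number is probably very small. Confidence is high about the wording and its inconsistency with 7d, 8 and section 6.11.2.1. It is lower about any real lack of protection, because some sections and the consent form cannot be read. No endpoint, analysis population or summary depends on this criterion.

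**What to change.** In inclusion criterion 9, replace the stated period with: *during treatment and for at least 30 days after the last dose of study drug*. This matches 7d and 8 and agrees with the reporting period in section 6.11.2.1. The consent form should be checked for the same period. The cost is one phrase, which can go into the next amendment; no visits, tests or patients are added.

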#### **3.2 Study Duration and Dates**

The total study participation/duration is approximately 18 weeks; up to 4 weeks for screening, followed by 12 weeks of dosing, and a follow-up visit 2 weeks after end of treatment.

The schedule of procedures and visits for the study is provided in [REDACTED]

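### Exclusion criterion 26 ends its live-vaccine window at screening, so the published entry criteria set no minimum gap between a non-VZV live vaccine given during screening and the first dose

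*Combined protocol and SAP*

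**What the plan says.** Section 4.2 sends sites to the Synopsis for the entry criteria, so the Synopsis list decides enrollment. Two of its exclusion criteria concern vaccines.

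- Criterion 26, on live vaccines in general: "Receipt of live vaccine within 4 weeks prior to screening".
- Criterion 25, on VZV only. It excludes patients with no recorded positive VZV IgG result, and also patients "who have completed VZV vaccination within 30 days prior to randomization".

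The length of screening is stated three times. Under Study Design, the Synopsis says the screening period "will last up to 4 weeks and is followed by a 12-week treatment period". Under Duration per Patient it gives "up to 4 weeks for screening, followed by a 12-week treatment period". Section 3.2 gives "up to 4 weeks for screening, followed by 12 weeks of dosing".

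Three other exclusion criteria might be thought to catch a vaccine given during screening:

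- Criterion 10: "Within 30 days prior to randomization, treatment of underlying disease other than those specifically listed in Section 6.12".
- Criterion 11: "Within 30 days or 5 half-lives (whichever is longer) prior to randomization receipt of any investigational agent".
- Criterion 33: "History of any clinically significant medical condition", where the investigator judges that it rules out participation.

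Section 4.1 requires every entry criterion to be met before randomization. Section 6.2 provides for a partial examination at check-in, to update the screening findings and record pre-treatment adverse events.

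**The concern.** A live-vaccine exclusion protects a patient from starting an immunomodulating drug soon after receiving a live organism. The interval that matters therefore runs from vaccine to first dose. Section 1.1.1 describes the drug class as acting by sequestering lymphocytes, and Section 6.11.1 treats lymphopenia as so expected that it is not recorded as an adverse event.

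Criterion 26 measures a different interval, from vaccine to screening. Exposures further from dosing are barred, while those closest to it are not mentioned. If nothing else in the protocol intervenes, a patient could receive a live vaccine the day before dosing and still satisfy every published criterion. What is at stake is individual safety, not any estimate or endpoint.

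**Working it through.** No figure in the plan needs reproducing; the check is date arithmetic followed by a reading of the neighboring criteria.

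**Inputs.** The look-back in criterion 26 is 4 × 7 = 28 days, ending at screening. The time from screening to first dose is S days, with S between 0 and 28 (Synopsis; Section 3.2). Let d be the number of days from vaccine to first dose.

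**What criterion 26 excludes.** It excludes vaccines given 0 to 28 days before screening, that is, S ≤ d ≤ S + 28. Vaccines given after the screening day and before the first dose, 1 ≤ d ≤ S − 1, are not covered. If the screening day itself is not counted as covered, one more day is open.

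| S | d excluded now (S to S + 28) | d left open (1 to S − 1) | Guaranteed interval, option A (28 + S) | Guaranteed interval, option B |
|---|---|---|---|---|
| 0 | 0 to 28 | none | 28 | 28 |
| 14 | 14 to 42 | 1 to 13 | 42 | 28 |
| 28 | 28 to 56 | 1 to 27 | 56 | 28 |

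Option A keeps the present window and adds the time from screening to first dose. Option B counts 4 weeks back from first dose instead.

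**The contrast at S = 28.** A vaccine 27 days before screening has d = 27 + 28 = 55 and excludes the patient. A vaccine on Day -1 has d = 1 and does not. The minimum interval that criterion 26 itself sets for a vaccine given after screening is therefore none.

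**Whether another published criterion closes the gap.**

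- Criterion 10 is confined to treatment of the underlying disease; a vaccine is not that.
- Criterion 11 is confined to investigational agents; a routine vaccine is not one.
- Criterion 33 concerns medical conditions and sets no vaccine interval.
- Criterion 25 counts back from randomization, which in this single-arm study I read as treatment start, but it covers VZV only.
- Section 4.1 fixes when the criteria must be satisfied. It does not move a window that is defined by screening.
- The check-in in Section 6.2 gives an opportunity to ask about vaccines but sets no rule.

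For non-VZV live vaccines, none of these supplies a minimum interval.

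**The case against.** The strongest objection is that the relevant text is withheld. Section 6.12, which inclusion criterion 4 and exclusion criterion 10 both cite for permitted treatment, is not in the public copy, and neither is the schedule of procedures. The published text also has no live-vaccine rule for the 12 weeks on drug, which fits the possibility that vaccines are dealt with in a withheld section. This stands. A reader might infer that the protocol as a whole permits live vaccination up to the first dose. The documents do not support that, because text withheld from the public copy cannot be treated as absent from the plan. What survives is narrower: a criterion that states its own time limit, in the list that decides enrollment, ends that limit at the wrong point.

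A second tempting inference is that an unfinished VZV vaccine series slips through, because criterion 25 speaks of completed vaccination. Its first limb already excludes anyone without a recorded positive VZV IgG. The only remaining case is a patient with positive IgG and an incomplete series, which is too narrow to carry weight.

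A third is that criterion 26 is the one criterion out of step. It is not. Of the 14 exclusion criteria with a stated look-back, 9 count from randomization (8, 9, 10, 11, 15, 17, 19, 25, 30), 1 from enrollment (7) and 4 from screening (2, 18, 23, 26). The anchors are mixed and no pattern follows. Criterion 23 shares the screening anchor, but criteria 7 and 17 also reach clinically significant infections arising during screening; non-VZV live vaccines have no such second criterion.

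Finally, the practical effect is small. The documents give no rate of live vaccination during screening, it is probably rare, and few patients are enrolled. This also stands, and it limits the severity.

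**Conclusion.** The point holds in limited form. For a non-VZV live vaccine given during a screening period of up to 28 days, the published entry criteria set no minimum interval before the first dose; at the longest screening, up to 27 days are left open. The conclusion rests on two readings: that the window in criterion 26 ends when screening starts, and that randomization in a single-arm study means treatment start. It is confined to the published criteria, and any harm is conditional on no withheld section barring live vaccines during screening. Severity is low: at most 20 patients (Section 3.1), with no endpoint, estimate or analysis affected.

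**What to change.** Extend criterion 26 to the first dose. There are two workable forms.

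- **Option A.** Keep "Receipt of live vaccine within 4 weeks prior to screening" and append: *or at any time between screening and first dose*. This loosens nothing and guarantees 28 + S days, so never fewer than 28. It is longer than the vaccine-to-dose reasoning strictly needs.
- **Option B, the minimum.** Replace the anchor so that the 4 weeks are counted back from the first dose. This guarantees 28 days for every patient. It admits some patients now excluded, for example one vaccinated 2 days before a 28-day screening period, who would be 2 + 28 = 30 days from vaccine at dosing.

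The documents state no required vaccine-to-dose interval, so the choice is a clinical one for the sponsor. Option A is the safer default because it only adds protection. If Section 6.12 or the schedule already bars live vaccines during screening, a cross-reference in criterion 26 is enough.

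The cost is one clause in the criterion and the matching line in the eligibility checklist. An occasional patient vaccinated during screening will be delayed or excluded.
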